Précis:	More rapid fluid removal (i.e. higher UF rate) is associated with adverse cardiovascular outcomes among maintenance hemodialysis (HD) patients. UF profiling may reduce UF-related cardiovascular complications. We will conduct a 4-period cross-over trial with 30 participants in which participants are alternated between UF profiling and standard HD therapy and key cardiovascular and patient-reported outcomes are assessed.
Objectives:	To investigate the comparative effect of UF profiling during HD and non-profiled conventional HD on select cardiovascular and patient-reported outcomes
Primary Endpoints	1) intradialytic hypotension, 2) troponin T change, 3) TTE-measured global longitudinal strain change
Population:	Adult individuals on maintenance HD for ≥ 3 months who have mean UF rates > 10 mL/h/kg in the screening period who receive HD at a UNC-associated dialysis clinic (Carolina Dialysis Carrboro, Siler City, Pittsboro, Mebane, or Sanford)
Phase:	Phase 2
Number of Sites enrolling participants:	5 (all sites are UNC-based: Carolina Dialysis Carrboro and Siler City)
Description of Study	Linear UF profiling is an HD technique in which the UF rate (fluid removal rate) is linearly decreased over the course of HD (starting UF rate = 1.33x the rate that would be needed at a constant UF rate to achieve the desired post-dialysis weight). The practice maximizes fluid removal during periods of greatest hydration and plasma oncotic pressure.
Experimental Intervention:	
Study Duration:	15 months
Participant Duration:	4 months (+ 6 week screening period)

SCHEMATIC OF STUDY DESIGN

2 INTRODUCTION: BACKGROUND INFORMATION AND SCIENTIFIC RATIONALE

2.1 BACKGROUND INFORMATION

United States HD patients have unacceptably poor outcomes with mortality rates greater than eight-fold those of individuals without kidney failure and symptom burdens on-par with those of cancer patients. Many difficult to modify factors such as co-morbid disease, chronic inflammation and poor nutrition contribute to the high morbidity and mortality experienced by HD patients. However, HD treatment factors also affect outcomes. Modifications of the HD procedure itself may represent feasible strategies to improve clinical outcomes. The rate of fluid removal during HD (UF rate) is a critical contributor to cardiovascular complications in HD patients. Higher UF rates are linked to greater morbidity and mortality. The mechanism likely relates to BP perturbations, myocardial ischemia, systemic inflammation, and other end-organ ischemic damage. In cases where fluid removal outpaces vascular refill rates, UF induces both subclinical end-organ hypoperfusion and frank hypotension. Hypoperfusion leads to regional myocardial hypoxia as evidenced by “stunning” on TTE and troponin elevation.

Hemodialysis procedural strategies, such as UF profiling, the practice of varying UF rates to maximize fluid removal during periods of greatest hydration and plasma oncotic pressure, may reduce UF-related cardiovascular complications and patient-reported symptoms. See section 2.2 for UF profiling rationale. The objective of this study is to investigate the comparative effect of UF profiling during HD and non-profiled conventional HD on select cardiovascular and patient-reported outcomes.

2.2 RATIONALE

UF profiling, the practice of varying UF rates to maximize fluid removal during periods of greatest hydration and plasma oncotic pressure, is one treatment modification that may reduce UF-related harm without necessitating reduction in interdialytic fluid intake or longer HD treatments. While UF profiling has been available for decades, it has not been adequately studied independently of sodium profiling. Sodium profiling uses a higher dialysate sodium concentration to increase plasma osmolality. While sodium profiling (\pm UF profiling) often reduces hypotension, it disadvantageously sodium-loads the patient. The resultant positive sodium balance leads to increased thirst, weight gain, and interdialytic hypertension. Sodium profiling has been dismissed as a viable treatment option due to these disadvantageous side effects. Alternatively, UF profiling may reduce UF-related hemodynamic instability and associated cardiovascular consequences without altering sodium balance. Hypotensive episodes occur when UF rates exceed plasma refill rates. UF profiling allows for lower UF rates later in the HD treatment when plasma refill rates are the slowest and hemodynamic instability risk the highest. Thus, UF profiling has the potential to improve hemodynamic stability without untoward sodium gains.

2.3 POTENTIAL RISKS AND BENEFITS

2.3.1 KNOWN POTENTIAL RISKS

The risks involved in this study are small. Patients will complete 2 study arms (2 phases of each): UF profiling and conventional dialysis. Both forms of dialysis are used in clinical practice and are considered standard of care. Other than the different fluid removal paradigms, patients will undergo routine dialysis as prescribed by their treating nephrologists. All HD carries a risk of low blood pressure, heart rhythm abnormality, electrolyte abnormality, and bleeding. Patients are exposed to these risks each time they undergo dialysis. Participation in this study will not increase these baseline risks. There are no known risks associated with UF profiling. All study monitoring is low risk and part of routine dialysis care. Blood draws for laboratory testing will be low volume and will not exceed a total of 20 mL/ patient. Blood draws will be performed by experienced dialysis nurses, and blood will be taken from the cannulated dialysis access (thus no additional cannulations will be necessary). The main risk associated with the blood tests is bruising or bleeding at the access.

2.3.2 KNOWN POTENTIAL BENEFITS

There is no additional direct benefit to the subjects participating. The results of this study may potentially benefit to future patients and their peers on dialysis. If individual participants experience improvement in UF-related cardiovascular risk or symptoms with UF profiling, UF profiling could be incorporated into their individual clinical dialysis prescriptions.

3 OBJECTIVES AND PURPOSE

The objective of this study is to investigate the comparative effect of UF profiling during HD and non-profiled conventional HD on select cardiovascular and patient-reported outcomes.

4 STUDY DESIGN AND ENDPOINTS

4.1 DESCRIPTION OF THE STUDY DESIGN

The study is a 4-period cross-over trial (see schematic of study design) in which participants are successively alternated between study arms across 4 periods with intervening washout periods, and treatment order is randomized. The study control arm is conventional HD: the patient's standard HD prescription (no UF profiling). The study experimental arm is conventional HD + linear UF profiling. Linear UF profiling will be specified as a linearly decreasing UF rate with a UF rate starting at 1.33 times the rate that would be needed at a constant UF rate to achieve the desired post-weight (Fresenius 2008K machine profile 2). After providing consent, patients will be randomly allocated to experimental or control treatment for period 1. Patients will undergo 9 treatments during each phase for a total of 18 conventional HD treatments and 18 UF profiled treatments. Patients will undergo 3 wash-out HD treatments between phases. The study will be double-blinded in that patients will not be informed of the treatment paradigm. Investigators, including those performing TTE interpretation, will be blinded to treatment paradigm. Ultrasonographers performing intra-HD TTEs will be blinded to treatment paradigm.

4.2.1 PRIMARY ENDPOINT

- 1) Intradialytic hypotension: measured on a per-treatment basis; defined as nadir systolic BP <90 mmHg
- 2) Troponin T change: measured at the 7th treatment of each phase; defined as pre-HD – post-HD troponin T (ng/mL) and percentage change (troponin T rise) $\geq 10\%$
- 3) Left ventricular global longitudinal strain (GLS) on TTE: measured at baseline and 30 minutes before HD end during 7th treatment in the first phase of each treatment type (once during conventional and once during UF profiled treatment); defined as % GLS change (intradialytic GLS – baseline GLS), see Appendix A for TTE protocol. A change $\geq 2.5\%$ indicates a clinically important change in GLS.

4.2.2 SECONDARY ENDPOINTS

- 1) Systolic BP change: measured on a per-treatment basis; defined as pre-HD – nadir intra-HD systolic BP (mmHg)
- 2) Nadir systolic BP: measured on a per-treatment basis; defined as the minimum intradialytic systolic BP (mmHg)
- 3) Target weight achievement: measured on a per-treatment basis: defined as post-HD weight within 1 kg of prescribed target weight.
- 4) Weight difference: measured on a per-treatment basis; defined as target weight – post-HD weight (kg)
- 5) Patient acceptance: measured after treatment 9 of each phase; response to the following question, "If recommended by your physician, would you be willing to adopt the HD prescription you have received during the last 9 treatments?"

6) TTE ejection fraction (EF): measured 30 minutes before HD end during 7th treatment in the first phase of each treatment type (once during conventional and once during UF profiled treatment); defined as % EF change (baseline – intradialytic EF), see Appendix A for TTE protocol

7) Patient-reported symptoms: measured after the 1st HD treatment each week; see Appendix B for data collection form.

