7.1.2 STANDARD OF CARE STUDY PROCEDURES

Standard HD treatments without UF profiling (control): Fresenius 2008K HD machines, a dialysate temperature of 37°C, and patients' standard blood and dialysate flows will be used. No sodium profiling will be used. Dialysate composition and HD medications will be per baseline prescription determined by the treating nephrologist. Total UF volume and target weight will be determined by the treating nephrologist.

Standard-of-care BP measurement: BPs will be machine-measured with an upper extremity cuff in the seated position pre- and post-dialysis and every 20 minutes during every dialysis treatment.

Standard-of-care weight measurement: Per routine practice, target weight will be estimated by the treating nephrologist. Pre- and post-dialysis weights will be measured before and after each treatment in the standing position.

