10.4 DESCRIPTION OF STATISTICAL METHODS

10.4.1 GENERAL APPROACH

By cross-over design, each participant will act as his or her own control, permitting between and within group comparisons. Analyses will be performed on an intention-to-treat and modified intention-to-treat basis, separately. Comparisons of values between HD treatments will be performed by repeated-measures analysis of variance (ANOVA; or non-parametric methods depending on data type) for continuous outcomes and generalized estimating equations for categorical outcomes. Analogous analyses will be performed in both the intention-to-treat and modified intention-to-treat datasets. All statistical estimates will be tabulated along with their corresponding 95% confidence intervals. All reported P values will be 2-sided; <0.05 representing significance. All hypothesis tests that are observed to be statistically non-significant will be interpreted as such and reported as being inconclusive. However, as this is a small, pilot study, the magnitude of estimates and the corresponding confidence intervals will be considered in the results interpretation.

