10.4.3 ANALYSIS OF THE SECONDARY ENDPOINT(S)

Comparisons of values for the binary secondary endpoints of target weight achievement, patient acceptance, and symptom occurrence between HD treatments will be performed using generalized estimating equations. Comparisons of values for the continuous secondary endpoints of pre-HD to nadir intradialytic HD systolic BP change, intradialytic nadir systolic BP change, target and post-HD weight difference, and TTE ejection fraction change will be performed using ANOVA or non-parametric methods depending on data type.

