Depending on the type of various endpoints, we propose to perform the following tests to test the difference between UF profile and conventional treatment.

- **Binary Outcomes**
 - We will perform repeated measure logistic regression by regressing the binary outcome on the treatment indicator and test if the coefficient before the treatment indicator is significant. Each subject will have a random intercept. The model is given by
$$\text{logit}(\text{outcome}) \sim 1 + \text{treatment} + (1|ID)$$
- **Continuous Outcomes**
 - We will perform repeated measure linear regression by regressing the continuous outcome (percentage outcome will be log-transformed) on the treatment indicator and test if the coefficient before the treatment indicator is significant. Each subject will have a random intercept. The model is given by
$$\text{outcome} \sim 1 + \text{treatment} + (1|ID)$$
- **Categorical Outcomes**
 - We will perform repeated measure multinomial regression by regressing the categorical outcome on the treatment indicator and test if the coefficient before the treatment indicator is significant. Each subject will have a random intercept. The model is given by
$$\text{multi-logit}(\text{outcome}) \sim 1 + \text{treatment} + (1|ID)$$

Quality Check

For patients who dropped out during the study, normalize endpoints to the same scale as the other patients, depending on the type of endpoints.

Sensitivity Analyses

1. Exclude participants who dropped out from all analyses.
2. Exclude participants who had endpoint data drawn "off-schedule" (troponin T, symptoms, etc.) from individual endpoint analyses.
3. Exclude participants who had an abnormality with their troponin T blood draw from troponin T-related analyses.
4. Test for difference by order of randomization (UF profiling --> conventional --> UF profiling --> conventional) vs. (conventional --> UF profiling --> conventional --> UF profiling)
5. Test for difference by clinic (site 1 vs. site 2)

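### Systolic BP change is analysed as a raw difference with no pre-HD covariate, which leaves avoidable session-to-session noise in the estimate

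*Combined protocol and SAP*

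**What the plan says.** Protocol section 4.2.2 lists two related secondary endpoints. The first is a fall: "Systolic BP change: measured on a per-treatment basis; defined as pre-HD – nadir intra-HD systolic BP (mmHg". The second is a level: "Nadir systolic BP: measured on a per-treatment basis; defined as the minimum intradialytic systolic BP (mmHg".

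For the fall, protocol section 10.4.3 ("Comparisons of values for the continuous secondary endpoints of pre-HD to nadir intradialytic HD systolic BP change") names ANOVA or a non-parametric method and no covariate. The SAP, under Primary Analysis, Continuous Outcomes, states: "We will perform repeated measure linear regression by regressing the continuous outcome (percentage outcome will be log-transformed) on the treatment indicator". Its model has an intercept, the treatment indicator and a random intercept per patient. None of the five SAP sensitivity analyses adds the pre-HD pressure.

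The covariate is already collected. Protocol section 7.1.2 says: "BPs will be machine-measured with an upper extremity cuff in the seated position pre- and post-dialysis and every 20 minutes during every dialysis treatment". The design supplies many sessions per patient (section 4.1): "Patients will undergo 9 treatments during each phase for a total of 18 conventional HD treatments and 18 UF profiled treatments".

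**The concern.** The patient random intercept removes stable differences between patients. It does not remove variation in pre-HD pressure from one session to the next within a patient. Subtracting the nadir from the pre-HD reading amounts to assuming that a session starting 10 mmHg higher also reaches a nadir 10 mmHg higher. If the nadir follows the starting pressure only partly, sessions that happen to start high show a larger fall for reasons unrelated to treatment, and that variation stays in the error term.

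What is at stake is mainly precision: the estimated effect of profiling on the fall is less precise than the collected data allow. This matters somewhat in a study of 30 completers whose results, according to protocol section 10.4.1, will be read through the size of estimates and their confidence intervals. A lesser issue is that part of any arm difference in starting pressure enters the estimated effect on the fall.

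**Working it through.** **Inputs.** From the documents: 30 completers (sections 5.3 and 10.5); 18 sessions per arm per patient (4.1); two-sided 0.05 (10.4.1); 80% power for 5.9 mmHg in nadir SBP with SD 8 (10.5). Not in the documents: the within-patient correlation r between pre-HD and nadir SBP across sessions, the SD of pre-HD SBP, and the SD of the change. Assumed here: r from 0.3 to 0.7 for the precision calculation and 0.2 to 0.8 for the pass-through; equal SDs first, then unequal.

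**The plan's own figure.** A two-sample t calculation with 30 observations per condition and SD 8 gives 80.2% power at 5.9 mmHg, and a detectable difference of 5.885 mmHg at 80% power. The stated figure reproduces. It concerns nadir SBP; no figure is given for the change endpoint, so it does not test this point.

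**Residual variance, equal SDs s.**
- Raw change: 2(1 − r)s²
- Adjusted for pre-HD SBP: (1 − r²)s²
- Ratio, adjusted to raw: (1 + r)/2

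| r | variance ratio | SE ratio | adjusted SE smaller by | equivalent extra sessions |
|---|---|---|---|---|
| 0.3 | 0.65 | 0.81 | 19% | 54% |
| 0.5 | 0.75 | 0.87 | 13% | 33% |
| 0.7 | 0.85 | 0.92 | 8% | 18% |

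The last column is 1/ratio − 1. Put the other way, the raw SE is 8% to 24% larger than the adjusted one (1/0.922 = 1.08; 1/0.806 = 1.24).

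**Simulation.** With 30 patients, 4 phases of 9 sessions and an assumed within-patient SD of 14 mmHg, the SE of the treatment effect fell from 0.995 to 0.810 (r = 0.3), 0.840 to 0.733 (r = 0.5) and 0.660 to 0.609 (r = 0.7), with no bias in either analysis. At r = 0.5 the formula gives 14 × √(2/540) = 0.85 for the raw score, which agrees. The difference detectable with 80% power, (1.96 + 0.84) × SE, moves from 2.8 × 0.840 = 2.35 to 2.8 × 0.733 = 2.05 mmHg.

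**Unequal SDs.** Let k be the pre-HD SD divided by the nadir SD, so that the slope of nadir on pre-HD SBP is b = r/k. In units of the nadir variance, the raw score has k² − 2rk + 1 and the adjusted analysis 1 − r². The difference is (k − r)², which is never negative and is zero when b = 1.
- k = 0.7, r = 0.7 (b = 1): 0.51 against 0.51, no gain.
- k = 1.5, r = 0.3 (b = 0.2): 2.35 against 0.91; SE ratio √(0.91/2.35) = 0.62, so 38% smaller.

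**Pass-through of a pre-HD difference.** With no treatment effect, an arm difference d in pre-HD SBP shifts the raw change by (1 − b)d. For d = 3 mmHg and equal SDs, that is 2.4, 1.5 and 0.6 mmHg at r = 0.2, 0.5 and 0.8. Simulation gave 2.39, 1.48 and 0.62, with the adjusted estimate at about 0.

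**Chance imbalance.** With independent sessions, the SE of the arm difference in mean pre-HD SBP is SD × √(2/(30 × 18)): 0.49 mmHg at SD 8, 0.85 at SD 14 and 0.97 at SD 16.

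**The case against.** The strongest objection concerns what the adjusted model estimates. Within each 9-session phase, 8 of the 9 pre-HD readings follow at least one session under that arm, so pre-HD SBP may itself be affected by treatment. That pre-HD SBP is already part of the endpoint does not make conditioning on it harmless. Algebraically, the treatment coefficient for the change adjusted for pre-HD SBP is minus the coefficient for the nadir adjusted for pre-HD SBP. Suppose profiling raised the nadir by 3 mmHg in total and pre-HD SBP by 2 mmHg, with slope 0.5. The fall as defined shrinks by 3 − 2 = 1 mmHg, while the adjusted model reports 3 − 0.5 × 2 = 2 mmHg. These answer different questions. This objection stands, and it is why the adjusted estimate needs its own label and the unadjusted results beside it.

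Other limits also stand. The saving rests on assumed correlations. It applies to session-level noise; variation between phases, or in how patients respond to treatment, would dilute the percentage, although the gain persisted in a simulation that included both. Nor is the raw change always noisier than the nadir. With equal SDs that holds only for r below 0.5; at r = 0.8 the simulated SEs, with SD 8, were 0.31 for the change and 0.49 for the nadir.

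A reader might infer two stronger claims. One is that a pre-HD difference between arms passes into the result in full. That needs a slope of 0, meaning the nadir does not track the starting pressure at all or the difference is pure reading error. The other is that regression to the mean biases the comparison. Here it adds noise only: each patient serves as his or her own control with 18 sessions per arm, and the ordinary SE already carries that noise.

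**Conclusion.** The point holds as a matter of precision. Endpoint 1 is a raw difference, no analysis text includes the starting pressure, and the reading is available at every session. Under equal within-patient SDs and r of 0.3 to 0.7, the adjusted SE is 8% to 19% smaller. With the unequal SDs tried, the saving ranges from nothing to about 38%.

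Sensitivity to pre-HD differences is secondary. The share carried through is 1 minus the slope of nadir on pre-HD SBP. Chance differences have an SE of only about 0.5 to 1.0 mmHg for SDs of 8 to 16, so a 2 mmHg gap would be 2/0.85 = 2.3 SE at SD 14, and a systematic cause should then be considered.

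The consequence is modest. This is one of seven secondary endpoints, nadir SBP is analysed separately, and a reader should not infer that the trial's power statement is affected: the 5.9 mmHg figure is for the nadir and does not change.

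**What to change.** In the SAP, under Continuous Outcomes, add for this endpoint only: SBP change on treatment, same-session pre-HD SBP centred on the patient's own mean over all study sessions, the patient's mean pre-HD SBP, and the patient random intercept. Label the treatment coefficient as the effect on the within-session fall at a given starting pressure.

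Report beside it the unadjusted change, the unadjusted nadir SBP, and mean pre-HD SBP by arm. State in advance how they will be read together: if pre-HD SBP differs systematically by arm, the adjusted estimate leaves out any effect acting through starting pressure, and the unadjusted results must be read alongside it. Section 10.4.3 should also be aligned with 4.2.2, since it calls the nadir endpoint a change while 4.2.2 defines a level.

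The cost is a few lines of SAP text, one additional model and one descriptive row. No new data are needed and the sample size is unaffected. The price in interpretation is the possible effect of treatment on pre-HD SBP after the first session of a phase.

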5.3 STRATEGIES FOR RECRUITMENT AND RETENTION

The recruitment goal is 36 participants (to account for drop-out) with study completion goal of 30 participants. The PI, a nephrologist, will identify eligible subjects from participating dialysis clinic (Carolina Dialysis Carrboro, Siler City) patient rosters and offer opportunity to participate in the study. If the patient does desire to participate in the research study, informed consent will be obtained by the PI or research staff. A study information sheet will be made available in the clinic for patients who desire additional information about the study. Participants will receive \$20 for their time spent participating in the baseline TTE procedure because it is the only TTE performed outside of participants' regular dialysis treatment time. Participants will be compensated \$45 for each 9 week treatment period and \$20 for the baseline period TTE (\$200 for full study completion).

Participants may miss study treatments. Missed study treatments will be considered "missed" and will not be made-up. For example, if a patient misses treatment #9 from arm 1, the patient will start wash-out treatments at the next treatment and will have missing data for treatment #9. The permeated design of the study arms (alternating conventional, UF profile, conventional, UF profile) was selected to maximize opportunities for data collection under each treatment paradigm. If participants are lost to follow-up (death, withdrawn consent, move to a new dialysis center), additional participants will be recruited until a study size of 30 participants is reached.

Based on the composition of the patient populations at the participating UNC sites, the expected sex breakdown is 50% male and 50% female and the expected enrollment of Hispanic or Latino participants is 10%. No exclusion by sex or by ethnic/ racial background will be made. There are no expected differences in the response to UF profiling across sex or racial/ ethnic groups. Children (individuals < 18 years) and vulnerable participants are not included in the study.

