5.4.2 HANDLING OF PARTICIPANT WITHDRAWALS OR TERMINATION

While participants will be encouraged to complete the study, they may withdraw from the study at any time and for any reason. Every effort will be made to determine why any participant withdraws from the study prematurely. This information will be recorded. Withdrawn subjects will be replaced, until 30 participants complete the study.

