7.2.2 OTHER ASSAYS OR PROCEDURES

TTE: Patients will undergo intradialytic TTE at baseline (within 6 weeks prior to study start) and 30 minutes prior to HD end ("peak stress") during treatment 7 of the first phase of each treatment type (once during conventional and once during UF profiled treatment) (1 TTE during UF profiled HD and 1 during control HD). Study TTEs will be performed by a trained sonographer with a Philips CX50 ultrasound system (Philips North America).

Blood volume monitoring: Blood volume monitoring will be performed continuously throughout each study treatment via a Crit-line™ (standard-of-care non-invasive relative blood volume monitoring tool used as part of standard dialysis treatments).

Plasma refill test: Using the blood volume monitor, a plasma refill test will be performed 10 minutes before HD end during the 7th treatment of each phase. At the start of the treatment, UF time will be set 10 minutes less than treatment time. When the dialysis UF ends, study staff will document the hematocrit (%) from the blood volume monitor, and when the treatment ends, document the blood volume monitor hematocrit (%) again. Plasma refill tests are part of the blood volume monitoring protocols at the selected units and are familiar to staff.

Patient acceptance: At the end of the 9th study treatment of each phase, study staff will ask the participant the following question: "If recommended by your physician, would you be willing to adopt the HD prescription you have received during the last 9 treatments?"

Symptom assessment: At the conclusion of the 1st study treatment each week, study staff will ask patients to complete a symptom questionnaire (Appendix B).

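### Patient acceptance is asked only after treatment 9 of each phase, so participants who leave mid-phase or miss that session can go unasked, and acceptance in an arm can be overstated

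*Combined protocol and SAP*

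**What the plan says.** Acceptance is secondary endpoint 5 in protocol section 4.2.2: "Patient acceptance: measured after treatment 9 of each phase". The procedure in section 7.2.2 has the same timing: "At the end of the 9th study treatment of each phase, study staff will ask the participant the following question". The question itself, "would you be willing to adopt the HD prescription you have received during the last 9 treatments", presupposes a completed phase.

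Section 5.3 does not allow missed treatments to be made up. Its example is the very session at which acceptance is asked: "the patient will start wash-out treatments at the next treatment and will have missing data for treatment #9".

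On leaving the study, section 5.4.2 provides for a reason but not for the acceptance question: "Every effort will be made to determine why any participant withdraws from the study prematurely". It then adds: "Withdrawn subjects will be replaced, until 30 participants complete the study". The planning figures are in section 5.3: "The recruitment goal is 36 participants (to account for drop-out) with study completion goal of 30 participants".

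On analysis, section 10.4.3 compares acceptance between treatments by generalized estimating equations. The SAP (Primary Analysis) uses a logistic model with a treatment term and a random intercept per participant. Sections 10.3 and 10.4.1 name intention-to-treat and modified intention-to-treat datasets but define neither. The SAP's Quality Check says to normalize endpoints for drop-outs, which has no clear meaning for a yes/no question that was never asked. Its first sensitivity analysis removes drop-outs from all analyses.

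**The concern.** The endpoint is meant to show whether patients would take up a prescription that they have tried. Someone who leaves part-way through a phase because of how the sessions feel is informative about exactly that, yet has no answer for that phase. What the plan yields is acceptance among those who were still attending at treatment 9.

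If leavers are less willing than stayers, the acceptance figure for that arm is too high. If such leaving is more common in one arm, or its leavers are more unwilling, the comparison favours that arm. Neither model repairs this when leaving depends on unwillingness that was never recorded. The only sensitivity analysis aimed at drop-outs moves further towards completers, and none goes the other way.

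A smaller gap concerns participants who stay in the study but miss treatment 9. They go into wash-out with no stated time at which to be asked. An answer not sought at the time may not be recoverable later.

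**Working it through.** **The plan's own figure.** Section 5.3 recruits 36 for 30 completers, an allowance of 6, or 6/36 = 16.7%. No drop-out rate is stated, so 36 cannot be derived independently; it agrees with 30/(1 − 1/6) = 36. The documents give no expected acceptance rate, and section 10.5 makes no power claim for acceptance.

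**Inputs from the documents.** There are 30 completers and two phases per treatment (section 4.1), with one answer per phase. Each arm therefore has 30 × 2 = 60 answers from completers.

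**Assumptions.** 90% of completers' answers are yes. Up to 6 participants leave before treatment 9 of their first phase of a treatment, and a proportion q of them would have said yes. Leavers add only the phase in which they left; any earlier answers are ignored here.

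**Formula.** With m recorded answers, a proportion p of them yes, and k unasked leavers:

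- observed acceptance = p
- acceptance among all who started the phases = (mp + kq)/(m + k)
- overstatement = [k/(m + k)] × (p − q)

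**One arm, both UF phases pooled (m = 60, p = 0.90, k = 6):**

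- q = 0: 54/60 = 90.0% against 54/66 = 81.8%, overstatement 8.2 points
- q = 0.40: (6/66) × 0.50 = 4.5 points
- q = 0.90: 0 points

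If the 6 instead leave in their second UF phase after one yes each, the figures are 60/66 = 90.9% against 60/72 = 83.3%, or 7.6 points.

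**A single phase on its own.** Here 27/30 = 90% compares with 27/36 = 75%, which is 15 points. That counts one answer per person, whereas the planned models use the answers from every phase.

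**UF profiling minus conventional (q = 0, 54/60 yes among completers in each arm):**

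| Leavers, UF / conventional | UF, all starters | Conventional, all starters | Bias in difference |
|---|---|---|---|
| 6 / 0 | 54/66 = 81.8% | 54/60 = 90.0% | +8.2 points |
| 4 / 2 | 54/64 = 84.4% | 54/62 = 87.1% | +2.7 points |
| 3 / 3 | 54/63 = 85.7% | 54/63 = 85.7% | 0 |
| 0 / 6 | 54/60 = 90.0% | 54/66 = 81.8% | −8.2 points |

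The sign depends wholly on where the leavers fall, and the documents do not say.

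**What the models can do.** A random-intercept likelihood model remains valid if leaving depends only on recorded answers. Ordinary GEE needs more: leaving must not depend on the answers at all, given the covariates in the model. Neither is valid when leaving depends on the unrecorded answer.

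**The case against.** A reader might infer more than the documents support.

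- **That acceptance of UF profiling is biased upward.** This needs leavers who are less willing and concentrated in UF phases, and nothing in the documents shows either. Conventional phases lose answers under the same rule, and patients are not told which treatment they receive. Section 10.2 hypothesises less hypotension with UF profiling, so leaving could as well be commoner under conventional treatment. The objection stands: the direction is open.
- **That replacement causes the problem.** Replacing a participant deletes nothing, and answers from completed phases remain in the main analysis. The gap is the question not asked, together with undefined analysis sets.
- **That the bias could reach 15 points.** On these assumptions that holds only for one phase analysed alone. Even the 8-point case is extreme, since it puts all 6 losses in one treatment and attributes all of them to it. Sections 5.3 and 5.4.1 list other causes, such as death, a move to another clinic and refusal of study procedures.
- **That missing treatment 9 must lose the answer.** Section 5.3 does not forbid asking later. SAP sensitivity analysis 2 excludes off-schedule endpoint data, which implies that the main analysis keeps them. This softens the point, but no time for asking is given, and that analysis does not name acceptance among its examples.
- **That every leaver should count as unwilling.** The control is the patient's own standard prescription, to which a leaver would ordinarily return, and the question is hypothetical. Such a rule does not belong in the main endpoint.

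It is also fair that this is one of seven secondary endpoints in a pilot, and that weekly symptom questionnaires capture some intolerance before withdrawal. Symptoms are not willingness, however, so the gap in this endpoint remains.

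**Conclusion.** The gap is real and modest. As written, the plan measures acceptance among participants present at treatment 9, with no answer from those who leave during a phase and no stated time for those who miss that session. Acceptance in an arm can be overstated if leavers are less willing. The between-arm difference can be biased either way, or not at all.

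The illustrative size is 0 to about 8 points for one arm with both phases pooled, and −8 to +8 points for the difference. It rests on three assumptions: 90% yes among completers' answers, 6 leavers, and leavers whose willingness ranges from none to that of completers. The 6 is a planning allowance rather than a cap, because recruitment continues until 30 complete.

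This is a cheap improvement. The primary endpoints and their conclusions are unaffected.

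**What to change.** **Protocol 4.2.2 and 7.2.2.** Ask the acceptance question at withdrawal when a participant leaves during a phase. If treatment 9 is missed, ask at the next attended session, before it starts. In both cases refer to this treatment phase in place of the last 9 treatments.

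**SAP.**

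- Report acceptance with everyone who started each phase accounted for, giving by arm the number not asked and the reasons.
- Add a sensitivity analysis that counts participants who left because of the treatment as not willing. Add best- and worst-case bounds by arm; for 6 unasked in the UF arm of the illustration these are 60/66 = 90.9% and 54/66 = 81.8%.
- State whether late answers count as off-schedule under sensitivity analysis 2.

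**Cost.** One question at a contact where staff already seek the reason for leaving, and a few sentences in the SAP. The downside is slightly different wording and timing for a few participants. No treatment or clinical rule changes.
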